8.9 Medical resource utilisation and health economics

Medical resource utilisation and health economics parameters are not evaluated in this study.

8.10 Guidelines, study assessments, and procedures during COVID-19 pandemic

In view of the ongoing and emerging novel coronavirus (COVID-19) pandemic spreading worldwide, the safety and well-being of our study participants is of primary importance. To protect the safety and well-being of study participants, this section will provide guidelines on study assessments and procedures during this period.

- 1 Every effort should be made to follow the clinical study protocol (CSP). Participant safety is paramount, and the investigator should continue to reassess the risk/benefit of continued study involvement for each study participant.
- 2 Investigational study sites must comply with local public health rules.
- 3 If a study participant is diagnosed with COVID-19 or is suspected to have COVID-19, they should follow the local area treatment and quarantine guidance.
 - (a) Please accurately document all diagnoses, procedures, assessments, dosing interruptions, and sequelae in the eCRFs. All AEs/SAEs should be reported in line with instructions for safety reporting documented in the CSP.
 - (b) If a COVID-19 AE/SAE is reported, the investigator should determine whether the participant's investigational product should continue, be interrupted, or stopped in accordance with the CSP.
 - (c) Patients with confirmed or suspected COVID-19 infection with moderate to severe symptoms may be at risk of dehydration or hypoxia. In case of such events the PI should consider IP interruption until symptoms improve.
- 4 If a study participant is unable to attend clinic visits, and/or receive study intervention, the site staff should keep in close contact with the study participant(s), preferably through telephone calls, to maintain awareness of their status.
- 5 If a patient cannot be seen on site, please consider the following options:
 - (a) Conducting the visits in the patient's home by study personnel or other trained professionals. In addition, third party vendor personnel may be utilised to conduct assessments.

- (b) Conducting the visit by phone, with urine samples, investigational product and urine sample collection containers shipped or otherwise transported between site and patient. The collection and analysis of safety blood samples at an alternative healthcare facility should be considered. Local lab results will not be collected or stored in the study database but will help the investigator to assess patient safety.
- (c) If labs collected for safety assessments cannot be collected for more than two consecutive visits between Visit 3 and Visit 7 including Visit 7 or for more than one visit between Visit 7 and Visit 14, the IP should be temporarily interrupted. With the absence of safety labs as described in the above case, IP will not be dispensed. However, if it is interrupted for greater than one month, the investigator should discuss with the medical monitor how to re-start treatment and titrate the IP to maintenance treatment. IP could be re-started during the unscheduled visits and then study participant should return to regular visits as per the study protocol.

References:

https://www.fda.gov/media/136238/download

https://www.ema.europa.eu/en/implications-coronavirus-disease-covid-19-methodological-aspects-ongoing-clinical-trials

https://www.ema.europa.eu/en/news/guidance-sponsors-how-manage-clinical-trials-during-covid-19-pandemic

9 STATISTICAL CONSIDERATIONS

9.1 Statistical hypotheses

Three hypotheses will be included in confirmatory testing for the primary objective. See Section 9.4.4 for a description of multiplicity control. The following hypotheses will be tested sequentially at two-sided alpha = 0.1 (treatments refer to initial dosing regimen prior to Protocol Version 5.0):

- Null hypothesis: No difference between high dose verinurad plus allopurinol compared to placebo on UACR at 6 months
- Alternative hypothesis: There is a difference between high dose verinurad plus allopurinol compared to placebo on UACR at 6 months
- Null hypothesis: No difference between high and intermediate dose verinurad combined plus allopurinol compared to allopurinol alone on UACR at 6 months
- Alternative hypothesis: There is a difference between high and intermediate dose verinurad combined plus allopurinol compared to allopurinol alone on UACR at 6 months

- Null hypothesis: No difference between allopurinol alone compared to placebo on UACR at 6 months
- Alternative hypothesis: There is a difference between allopurinol alone compared to placebo on UACR at 6 months

No other comparisons between treatment groups for the primary and secondary objectives will be adjusted for multiplicity.

9.2 Sample size determination

The estimated sample size of 145 patients per arm (initial dosing regimen) will yield 80% power to detect a 25% reduction in UACR for the high dose of verinurad + allopurinol compared to placebo (treatment difference of approximately -0.29 on the natural log scale) at the two-sided alpha level of 0.1, assuming a standard deviation of 1.0 on the natural log-scale. A total of 725 patients (145 patients per arm [initial dosing regimen]) must be randomised. The standard deviation estimate is based on the results of Study D5495C00007.

For the MRI substudy, a sample size of 30 in each arm (initial dosing regimen) will have at least 80% power to detect a difference (high dose verinurad + allopurinol vs. placebo) in means of 0.05 in renal arterial resistive index assuming that the common standard deviation is 0.05 with a 0.05 two-sided significance level. The standard deviation of 0.05 is based on data published by Leoncini et al 2002.

9.3 **Populations for analyses**

For purposes of analysis, the following populations are defined in Table 16:

Population	Description
Enrolled	All patients who sign the main ICF
Randomised set	All patients who are randomised
Full Analysis Set	All randomised patients
PPS	The per-protocol analysis set is a subset of the Full Analysis Set consisting of all patients who do not violate the terms of the protocol in a way that may affect the primary efficacy endpoint significantly. All decisions to exclude patients from the per-protocol analysis set will be made prior to the un- blinding of the study.
Efficacy analysis set	Full analysis set
Safety analysis set	All patients who had at least 1 dose of IP.
PK set	All patients who received allopurinol and verinurad treatment and have at least one post-dose plasma concentration measurement of verinurad at a scheduled time point

Table 16Analysis populations

ICF Informed consent form; IP Investigational product; PK pharmacokinetic

9.4 Statistical analyses

All personnel involved with the analysis of the study will remain blinded until database lock.

Analyses will be performed by a CRO designated by AstraZeneca. A comprehensive statistical analysis plan (SAP) will be developed and finalised before the first interim analysis and will describe the subject populations to be included in the analyse and procedures for accounting for missing data. This section is a summary of the planned statistical analyses. Any deviations from this plan will be reported in the CSR.

9.4.1 Endpoints

9.4.1.1 Primary endpoint

• Change from baseline in UACR at 6 months

9.4.1.2 Secondary endpoints

- Change from baseline in UACR at 6 and 12 months
- Change from baseline in sUA at 6 and 12 months
- Change from baseline in estimated glomerular filtration rate at 6 and 12 months
- Change from baseline in creatinine at 6 and 12 months
- Change from baseline in cystatin-C at 6 and 12 months

AstraZeneca

9.4.2 Efficacy analyses

All efficacy analyses will be performed using the Full Analysis Set (FAS) unless otherwise specified. In addition, the primary efficacy analysis will be performed using the Per Protocol Set as a sensitivity analysis.

Standard descriptive statistics comprise (but are not limited to) number of observations, mean value, standard deviation, coefficient of variation (or CV, for natural log-normal data), median value, minimum and maximum values.

9.4.2.1 Primary efficacy analysis

The primary efficacy variable is the change from baseline in UACR at 6 months (Week 34, ie, 26 weeks of treatment following an 8-week titration phase). Primary analyses will be performed on the FAS population, which consists of all randomised patients regardless of

treatment discontinuation. In other words, post-discontinuation data will be collected and included in the primary analysis. Details on how to handle missing data will be provided in the SAP.

In addition to analysis of the hypotheses in Section 9.1, the primary efficacy variable will be analysed comparing (initial dosing regimen):

- Intermediate dose verinurad plus allopurinol with placebo
- Low dose verinurad plus allopurinol with placebo
- High dose verinurad plus allopurinol with allopurinol alone
- Intermediate dose verinurad plus allopurinol with allopurinol alone
- Low dose verinurad plus allopurinol with allopurinol alone

The analysis of change in UACR from baseline to Week 34 will be conducted on the natural log-transformed UACR values using a repeated measures mixed model.

The analysis model will include the fixed categorical effects of treatment, week, DM status yes or no, microalbuminuria or macroalbuminuria, NT-proBNP < or \geq 360 pg/mL, use of SGLT2 yes or no, and treatment-by-week interaction as well as the continuous fixed covariates of baseline log(UACR) and baseline log(UACR) by-week interaction. An unstructured matrix for the within patient error variance-covariance will be used. The denominator degrees of freedom will be calculated according to the Kenward-Roger method. A number of back-up models will be defined in the SAP in case of non-convergence of the preferred model or other issues.

The least squared mean change from baseline to 6 months in the log-transformed UACR will be calculated by treatment with its 95% confidence intervals. The least squared mean difference between the treatments will be calculated with its 95% confidence interval. P-values of the treatment differences between active treatment group and placebo/comparator will also be calculated.

The above least squared mean change from baseline (and the 95% confidence interval) for each treatment will be exponentiated to yield the geometric mean ratio from baseline for each treatment with its 95% confidence interval at the original scale of UACR. The least squared mean difference between the active treatments and placebo/comparator (and its 95% confidence interval) will also be exponentiated to yield the geometric mean ratio between the 2 treatments at each visit and its 95% confidence interval at the original scale of UACR. Percent change from baseline will be derived from the geometric estimated mean ratio by ([geometric mean ratio] - 1) \times 100%.

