The Phase 2a study D5495C00007 was performed using 9 mg verinurad given as the ER8 capsule and 80 mg febuxostat administered once daily in combination for 24 weeks. The primary endpoint was UACR at 12 weeks.

Sixty patients were randomised. At enrolment, the treatment arms in study D5495C00007 were generally balanced with regards to common clinical parameters.

The study met the primary endpoint at 12 weeks. UACR was significantly reduced by 39.4% for patients randomised to be treated with verinural and febuxostat compared to placebo (p=0.0747). The comparison between the active arm and the control arm indicated statistical significance was achieved, considering the predetermined alpha (0.1). The effect on UACR was rapid, with full effect achieved at the first on-treatment assessment time point at 1 week, and did not appear to be driven by outliers. The therapeutic effect persisted with an LS mean of percent change from baseline in UACR compared to placebo (90% CI) -49.26 (-68.206, -19.009) at Week 24.

Mean baseline eGFR in the trial was 59 and 68 mL/min/ 1.73 m^2 in the active and control arms, respectively. There were no changes in eGFR in either arm, either at the early or late assessment time points. However, considering the limited sample size, eGFR variability, and short duration of treatment, this is not unexpected. Overall the treatment was well tolerated and safety findings in the study were consistent with the known safety profile of the drug.

The overall clinical evidence suggests that the combination of verinurad and XOI has clinical benefit and an acceptable safety profile in CKD patients and that further development is warranted. Hence, a global, randomised, Phase 2b study is planned to evaluate the efficacy and safety of verinurad and allopurinol in patients with CKD and hyperuricaemia.

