4.1.2.3 Week 0 (Visit 3)

- Collect first morning void samples from 3 days before visit (for primary CCI biomarkers)
- Review demography information
- Update concomitant medication
- Record medically important events as medical history
- Perform brief PE
- Record vital signs
- Record weight
- Obtain electrocardiogram (ECG)
- Obtain blood samples for clinical chemistry and haematology, efficacy assessments (s-UA, creatinine, eGFR, Cystatin C, NT-proBNP).
- Genetics sampling for some patients
- · Obtain urine samples for safety assessment (dipstick urinalysis
- Conduct renal MRI and PWV evaluation for patients who consented to participate in MRI sub-study prior to randomisation
- Reactive hyperaemia evaluation

- Perform pregnancy urine dipstick test for women of childbearing potential; after 2 positive urine tests, a serum pregnancy test is to be done by central laboratory
- Review inclusion/exclusion criteria
- Randomise patients via IVRS/IWRS transaction
- Dispense titration Step-1 dose
- Dispense containers for morning voids

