4.2 Scientific rationale for study design

The purpose of the study is to establish the dose of verinurad combined with allopurinol 300 mg once daily that will elicit the desired response; ie, reduction in UACR at 6 months. UACR is a measurement of albuminuria, it was chosen because changes in UACR can be detected early in response to treatment, and these changes, if substantial, correlate with progression of CKD, deterioration in eGFR, and hard outcomes. Therefore, change in UACR is regarded as an appropriate endpoint. In this study, change in UACR at 6 months of treatment is the primary endpoint for the efficacy evaluation of treatment with the combination of verinurad and allopurinol vs. placebo. A key secondary objective is evaluation of verinurad plus allopurinol on the reduction in UACR at 12 months. Additional secondary endpoints include changes from baseline in sUA, eGFR, cystatin C, creatinine and NT-proBNP. Further, standard safety parameters such as AEs, SAEs, and laboratory evaluations will be employed to assess the safety profile of the study drugs. Verinurad, allopurinol and oxypurinol plasma concentrations over time will also be measured.

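### The primary UACR model leaves out baseline eGFR, which is measured in every patient before dosing; adding it is a small, almost cost-free gain in precision

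*Supplement*

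**What the plan says.** Section 9.4.2.1 sets out a repeated measures mixed model on log-transformed UACR. Its categorical terms are treatment, week, diabetes status, micro- or macroalbuminuria and NT-proBNP split at 360 pg/mL. The list closes with "use of SGLT2 yes or no, and treatment-by-week interaction as well as the continuous fixed covariates of baseline log(UACR) and baseline log(UACR) by-week interaction". Baseline eGFR is not in it.

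The value is available. Table 1 schedules eGFR and NT-proBNP at Visits 2 and 3, and Section 4.1.2.3 has blood drawn at Week 0 for "efficacy assessments (s-UA, creatinine, eGFR, Cystatin C, NT-proBNP"), before the first dose is dispensed.

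The plan uses eGFR elsewhere:

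- Section 5.1.2 sets a floor of 25 mL/min/1.73 m² and no ceiling.
- Sections 4.1.2.5 and 6.1.1 make the step-3 dose conditional on eGFR of at least 30 at Visits 3 and 4.
- Appendix F 2 applies different renal monitoring and discontinuation rules above and below a baseline eGFR of 40.
- Section 9.4.2.4 defines two subgroup analyses by it, one by CKD stage and one split at 60.

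On power, Section 9.2 says: "The estimated sample size of 145 patients per arm (initial dosing regimen) will yield 80% power to detect a 25% reduction in UACR". It puts the effect at about -0.29 in logs. The calculation is made "at the two-sided alpha level of 0.1, assuming a standard deviation of 1.0 on the natural log-scale". On where that SD comes from, the section says: "The standard deviation estimate is based on the results of Study D5495C00007".

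**The concern.** A baseline covariate fixed in advance can reduce residual variance in a randomised comparison without inflating type I error. Baseline eGFR is a natural candidate here. It describes the disease under study, should span a wide range, and bears on the dose a patient can reach and on when treatment stops. The plan treats it as important enough for two subgroup analyses, but the main model takes no account of it.

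Adjustment also guards against chance imbalance. In the Phase 2a study described in Section 2.1, with 60 patients, mean baseline eGFR was 59 in the active arm and 68 in the control arm, although the arms were called generally balanced. With 145 per arm such differences would be smaller on average.

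What is at stake is some precision in the primary comparison, from data the trial already collects. The validity of the analysis is not in question.

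**Working it through.** **Inputs (Section 9.2).** n = 145 per arm; 25% reduction, δ = ln(0.75) = -0.2877, which the protocol rounds to -0.29; SD 1.0 on the natural log scale; two-sided alpha 0.1, so the critical value is 1.645.

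**Step 1: reproduce the stated power.** The standard error of the difference is 1.0 × √(2/145) = 0.1174. With δ = 0.2877 the standardised effect is 0.2877/0.1174 = 2.450, and power is Φ(2.450 - 1.645) = 78.9%. With δ = 0.29 it is 79.5%. A noncentral t calculation gives 78.8% and 79.3%. All round to the stated 80%, so the plan's own figure holds.

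**Step 2: effect of a further covariate.** If added covariates explain a share R² of the variance left by the current model, the SD becomes √(1 - R²), and the trial behaves as if it had 145/(1 - R²) patients per arm. The documents give no R² for eGFR or for continuous NT-proBNP, so the values below are assumptions. Here δ = ln(0.75), with complete data.

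| Assumed added R² | Power, normal | Power, t | Equivalent n per arm |
|---|---|---|---|
| 0 | 78.9% | 78.8% | 145 |
| 1% | 79.3% | 79.1% | 146.5 |
| 3% | 80.0% | 79.9% | 149.5 |
| 5% | 80.7% | 80.6% | 152.6 |

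The gain over 1-5% is 0.3 to 1.8 points, or 1.5 to 7.6 patients per arm. The R² is for eGFR and continuous NT-proBNP together; eGFR alone would supply only part of it.

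**Step 3: is the SD already adjusted?** Section 9.2 does not say. Section 2.1 reports a 39.4% reduction with p = 0.0747. The implied standard error is |ln(0.606)|/1.78 = 0.281. The Week 24 90% confidence interval implies 0.284. Then SD = SE/√(2/n), which is 1.09-1.10 at an assumed 30 per arm and 0.99-1.00 at an assumed 25. The planning SD of 1.0 may therefore be a model-based figure that already carries some baseline adjustment. The R² above must be read as what is gained beyond that.

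**Step 4: the NT-proBNP split.** For a normal covariate with a linear effect, a two-level split keeps φ(z)²/[p(1 - p)] of the explained variance: 0.64 with the cut at the median and 0.49 at the 80th percentile. This applies only to NT-proBNP's own share of an R² that is unknown and probably small.

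**The case against.** The strongest reply is that this is a preference about covariates and not a fault. The model already adjusts for continuous baseline log(UACR) with its week interaction, and for diabetes, albuminuria class, NT-proBNP and SGLT2 inhibitor use. The baseline of the outcome is usually the strongest predictor, so little may be left for eGFR to explain. That stands, and it is why the gain is put no higher than a point or two.

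Four stronger readings are tempting, and the documents do not support them.

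- *Power has slipped below 80% and eGFR would restore it.* It has not: 78.8-79.5% is 80% to rounding. Section 9.2 has no dropout allowance and Section 6.3 no replacement of withdrawals, but that is a separate matter. At an assumed 10% or 20% loss of Week 34 data, ignoring what the repeated measures model recovers, power would be 75.1% or 70.7%. The added R² needed to return to 80% would then be 12.7% or 22.4%, which nothing in the documents makes plausible.
- *The protocol itself says that eGFR predicts UACR change.* Section 4.2 says substantial changes in UACR "correlate with progression of CKD, deterioration in eGFR, and hard outcomes". That supports UACR as an endpoint. It does not say that baseline eGFR predicts the change in UACR. Nor does use of eGFR in subgroups or dosing rules prove prognostic value.
- *The NT-proBNP category is wrong.* Section 6.3 names no strata and the SAP is not shown. If the category is a randomisation stratum, it belongs in the model.
- *Every secondary model should gain the term.* For eGFR as outcome it would duplicate the outcome's own baseline, and for creatinine it would nearly do so, because eGFR is calculated from creatinine.

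Timing is a fair objection too. Section 9.4 has the SAP finalised before the first interim analysis, and Section 4.1.1 reports a blinded interim in September 2020. The change therefore needs a documented amendment, not a wording edit. Section 9.5 keeps the study team blinded, so the amendment can still be made without knowledge of treatment effects.

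**Conclusion.** The point holds as an optional improvement. The protocol gives the primary covariate list in full and leaves missing-data handling and back-up models to the SAP, so the omission of baseline eGFR is a stated choice and not a gap left for later. Using it would take no new data and about one degree of freedom.

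The size is modest and unproven: about 0.3-2 points of power, or roughly 1-8 patients per arm. That rests on an assumed 1-5% of residual variance explained by eGFR with continuous NT-proBNP, complete Week 34 data, and SD 1.0 as the residual SD of the current model. There is no error in the planned analysis and no demonstrated loss of power.

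**What to change.** By a documented SAP amendment, decided by blinded staff before the Week 34 interim analysis:

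- Add baseline log(eGFR) as a continuous covariate to the primary UACR model, and to the 12-month UACR and sUA models. Take it from pre-dose values only: Visit 3, or Visit 2 if Visit 3 is missing.
- Do not add it to the eGFR, creatinine or cystatin-C models. Each should carry its own baseline.
- Replace the 360 pg/mL category by continuous log(NT-proBNP) only if the category is not a randomisation stratum. If it is, leave it as it stands.

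The cost is about one degree of freedom out of some 725 patients and one SAP amendment. Replacing the NT-proBNP category would use no further degree of freedom.

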Efficacy measurements		•									
sUA, creatinine, eGFR, Cystatin C, NT-proBNP		х	x	х	х	x	х	х	х	х	Section 8.1
UACR - First morning void samples from 3 days before visit		x	x	х	x	x	х	x	х	x	Section 8.1
CCI											
CCI											
CCI											
Optional genetics sampling	•	•									
Blood sample			X								Section 8.7
Study treatment dispensing ⁱ											
Randomisation			х								Section 6.3
Titration step 1 dose dispensed			Х								Section 6.1
Titration step 2 dose dispensed				х							Section 6.1
Final (Titration step 3) dose dispensed					Xj	Xj	Xj	Xj	Xj	X ^{j,b}	Section 6.1

Table 1 Schedule of activities (SoA), screening and treatment period

CONFIDENTIAL AND PROPRIETARY

Visit	1 (Pre- Screening)	2 (Screening)	3 (Randomis ation)	4	5	6	7	8 (Primary Analysis)	9 ^a	10 ^a See EOT visit in Table 2	Details in CSP section or Appendix
Week	-6 to -1	-4 to 0	0	4	8	12	20	34	47	60	
Window			NA	±7d	±7d	±7d	±7d	±7d	±7d	±7d	
Study treatment returned				х	Х	x	х	x	х	х	Section 6.2

Table 1 Schedule of activities (SoA), screening and treatment period

CSP Clinical study protocol; eGFR Estimated glomerular filtration rate; EOT End of treatment; FMV First morning void; FU follow up; IP Investigational product; CCI NA Not applicable; NT-proBNP N-terminal pro-brain natriuretic peptide; PK Pharmacokinetic; PWV Pulse wave velocity; sUA Serum uric acid; UACR urinary albumin to creatinine ratio

At the time of implementation of Protocol Version 5.0 (refer to Section 4.1.1 for description of implementation), a new dosing regimen will be introduced to assess the higher dose of 24 mg verinurad. Patients in the 3 mg verinurad cohort who will have Visit 9 planned after the amendment is implemented in the respective country will be switched to 24 mg dose at Visit 9. Patients will only be allowed to switch to the new dosing regimen's treatments introduced under Protocol Version 5.0 if the patient's eGFR was \geq 30 mL/min/1.73m² at Visit 8. Management of patients with eGFR <30 mL/min/1.73m² at Visit 9 should be discussed with the medical monitor.

Patients who do not tolerate the new dosing regimen will be down-titrated to the initial dosing regimen (ie, patients on 24 mg will be down-titrated to 3 mg, and patients in other cohorts will not be dispensed the matching placebo capsule).

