4.1.2.2 Week -4 to -0 – screening (Visit 2)

- Collect first morning void samples from 3 days before visit
- Obtain signed full ICF
- Record serious adverse events (SAEs)
- Obtain demography information

- Obtain full medical history with note of comorbidities
- Record concomitant medication
- Perform full physical examination (PE)
- Obtain vital signs
- Obtain height and weight
- Obtain 12-lead electrocardiogram (ECG)
- Obtain blood samples for clinical chemistry and haematology, and efficacy assessments (s-UA, creatinine, eGFR, Cystatin C, NT-proBNP)
- Obtain blood sample for HLA-B*5801 allele genotyping for all patients prior to randomisation
- Obtain urine samples for safety assessment (dipstick urinalysis)
- Perform pregnancy urine dipstick test for women of childbearing potential; after 2 positive urine tests, a serum pregnancy test is to be done by central laboratory
- Evaluate all inclusion/exclusion criteria
- Confirm eligibility for renal MRI evaluation for patients who consented to participate in MRI sub-study prior to randomisation
- IVRS/IWRS (Interactive Voice/Web Response system) transaction
- Dispense containers for morning voids

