8.1.1 Primary outcome - UACR

The ratio of urinary albumin to urinary creatinine (milligrams of albumin per grams of creatinine) will be assessed by a central laboratory. The mean ratio will be reported for each time point based on all samples collected (FMV sample 1, 2, and 3).

First morning void urine samples will be used for assessment of UACR. Patients will receive a urine sample collection kit allowing them to collect the first morning void urine on 3 consecutive days. Collected samples will be refrigerated until they can be brought to the study site for further processing in accordance with the laboratory manual. Ideally the urine samples should be collected 2 days before, the day before and on the day of a study visit to minimise storage and transportation of collected samples.

If a patient has forgotten to collect one or more of the samples before a visit, then the samples should be collected on the up-to-3 consecutive days following the visit instead (with exception for the randomisation visit urine samples, which must be collected before treatment is started).

In the absence of results from 3 analysed samples, the UACR for a time point will be calculated based on the available results.

Urine samples collected for assessment of UACR CC must not be confused with urinalysis samples collected at study site during visits for assessment of safety parameters and pregnancy testing.

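### UACR is collected before treatment at both Visit 2 and Visit 3, but the primary model names one baseline log(UACR) covariate and the protocol does not say which visit it comes from; adding Visit 2 as a second covariate may gain a little precision

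*Supplement*

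**What the plan says.** **Collection.** Table 1 (Section 1.1) has the row "UACR - First morning void samples from 3 days before visit" marked at Visit 2 and again at Visit 3. Section 4.1.2.2 repeats it for screening: "Collect first morning void samples from 3 days before visit". Section 4.1.2.3 does the same for the randomisation visit, and Section 8.1.1 requires the randomisation-visit samples to be taken before treatment starts.

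**Summary per visit.** Section 8.1.1: "The mean ratio will be reported for each time point based on all samples collected (FMV sample 1, 2, and 3". Visits 2 and 3 therefore yield two separate pre-treatment values, each a mean of up to three voids.

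**Model.** Section 9.4.2.1 specifies a repeated measures model on log UACR. Its continuous covariates are "continuous fixed covariates of baseline log(UACR) and baseline log(UACR) by-week interaction". It also has categorical terms, including micro- versus macroalbuminuria. Visit 2 UACR is not listed as a term.

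**Definition of baseline.** None is given for UACR. Inclusion criterion 9 asks for at least two first-morning voids before randomisation but names no visit. By contrast, Appendix F 2 defines baseline creatinine for renal safety from all pre-randomisation values.

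**Sample size.** Section 9.2: "The estimated sample size of 145 patients per arm (initial dosing regimen) will yield 80% power to detect a 25% reduction in UACR". The effect is put at a log difference of about -0.29, and 80% power is claimed with alpha 0.1 (two-sided) and an SD of 1.0 for log values. On the SD: "The standard deviation estimate is based on the results of Study D5495C00007".

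**The concern.** UACR varies from visit to visit within a patient. One visit's value, even averaged over three voids, measures the patient's underlying level with error, and the part of the level it misses stays in the residual of the primary model. A second pre-treatment value is already collected from every patient. If it predicts Week 34 beyond what Visit 3 predicts, leaving it out makes the primary comparison less precise than the collected data allow.

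The comparison of high dose with placebo is the first step of the hierarchy, so its precision affects whether the other two confirmatory hypotheses are tested at all. Section 9.2 adds no allowance for dropout, and Section 6.3 says withdrawn patients are not replaced. Precision that needs no extra sampling is therefore worth having.

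**Working it through.** **1. The plan's own figure.** Inputs from Section 9.2: n = 145 per arm, two-sided alpha 0.1, SD 1.0, 25% reduction, so ln(0.75) = -0.2877 (stated as about -0.29). The noncentrality is 0.2877 / sqrt(2/145) = 2.45.

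| Difference | Power, t-based | Power, normal approximation |
|---|---|---|
| ln 0.75 | 78.8% | 78.9% |
| 0.29 | 79.4% | 79.5% |

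The stated 80% is essentially reproduced.

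**2. Gain if Visit 2 and Visit 3 measure the same underlying level.** Assumptions, none of them in the documents: between-patient SD of log UACR (sb) 1.0 to 1.5, and visit-to-visit SD 0.3 to 0.6 (variance ve). Section 9.2 does not say what the SD of 1.0 refers to; here it is taken as the residual SD with one baseline visit. With k baseline visits,

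residual variance = drift + ve + [sb² − sb⁴/(sb² + ve/k)],

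where drift is set so that k = 1 gives 1.0.

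- Low end, sb = 1.0, visit SD 0.3 (ve = 0.09). The bracket is 1 − 1/1.09 = 0.083 for k = 1 and 1 − 1/1.045 = 0.043 for k = 2. Residual variance falls by 0.040, to 0.960.
- High end, sb = 1.5, visit SD 0.6 (ve = 0.36). The bracket is 2.25 − 5.0625/2.61 = 0.310 for k = 1 and 2.25 − 5.0625/2.43 = 0.167 for k = 2. Residual variance falls by 0.144, to 0.856.

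t-based power at 145 per arm goes from 78.8% to 80.2% (low end) or 84.0% (high end).

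**3. Letting the level drift between Visits 2 and 3.** The formula above puts all drift after Visit 3, although the two visits may be up to four weeks apart. If drift accrues at a constant rate, with the Visit 2 to Visit 3 gap taken as 4 weeks against 34 weeks from Visit 3 to Week 34, the reduction is about 2.5% to 14% and power about 79.7% to 83.7%.

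**4. Less favourable correlations.** Write rb for the correlation of Visits 2 and 3, r3 for Visit 3 with Week 34, and r2 for Visit 2 with Week 34. Relative to total variance, the residual is

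- Visit 3 only: 1 − r3²
- both as covariates: 1 − (r3² + r2² − 2·r3·r2·rb)/(1 − rb²)
- plain mean: 1 − ((r3 + r2)/2)² / ((1 + rb)/2)

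The table gives variance relative to Visit 3 only, with power by the normal approximation (78.9% for Visit 3 only).

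| rb, r3, r2 | Both as covariates | Plain mean |
|---|---|---|
| 0.90, 0.80, 0.80 | 0.906 (82.3%) | 0.906 (82.3%) |
| 0.80, 0.70, 0.65 | 0.956 (80.5%) | 0.968 (80.1%) |
| 0.90, 0.75, 0.70 | 0.993 (79.2%) | 1.021 (78.2%) |
| 0.90, 0.80, 0.72 | 1.000 (78.9%) | 1.089 (75.9%) |

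In the last row r2 = rb × r3 (0.72 = 0.90 × 0.80), so Visit 2 adds nothing once Visit 3 is known. The two-covariate model then loses nothing beyond a few degrees of freedom, whereas the plain mean raises the variance by 9%.

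**5. An optimistic case, not relied on.** If all three correlations were equal (0.5 to 0.95), the reduction would be 11% to 24%. Visits 2 and 3 lie within weeks of each other and Week 34 is months later, so equal correlation is unlikely.

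**The case against.** The strongest reply is that nothing here is wrong. A baseline-adjusted repeated measures model on log UACR is valid, the baseline value is already a mean of up to three voids, and the micro/macroalbuminuria factor may carry some of the screening information. That stands. Restriction to 30–5000 mg/g at entry could shrink the gain further.

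Three stronger readings are tempting, and the documents support none of them.

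- *The model uses a single-visit baseline and discards Visit 2.* Per-visit averaging and the rule on randomisation-visit samples point to Visit 3, but baseline UACR is not defined. Section 9.4 calls itself a summary and defers to an SAP that is not shown, which may define baseline from all pre-randomisation voids.
- *The trial is underpowered and needs this repair.* Power is 79.4% at the stated difference of about 0.29. If the SD of 1.0 were the SD of change rather than the residual SD, baseline adjustment with one visit would already give 82.6% at an assumed correlation of 0.8.
- *Averaging the two visits would do equally well.* The table above shows that it can lose precision.

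It is also fair to say that the change is not quite one line. Section 5.4 allows a repeat of an out-of-range assessment and screening up to twice, so some patients may have more than one Visit 2 set, some of them kept because they fell in range. The second covariate also enlarges an unstructured model for which Section 9.4.2.1 already foresees possible non-convergence.

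**Conclusion.** The point holds as an efficiency gain, not as an error or a needed power repair. Two pre-treatment UACR values are collected, the listed model has one baseline term, and which visit supplies it is not stated in the protocol. Adding the Visit 2 value as a covariate uses data already in hand, introduces no bias and has little downside.

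The size is an assumed range: residual variance lower by about 0% to 14%, and power at 145 per arm of about 79% to 84% against 78.8%. This rests on the SD of 1.0 being the residual SD with one baseline visit, on a difference of ln 0.75 with complete data, and on variance components and correlations that the documents do not give. Blinded study data could narrow the range.

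**What to change.** 1. State in Section 9.4.2.1 and the SAP that baseline for the change score is the Visit 3 mean UACR, log-transformed.
2. Add Visit 2 log(UACR) and its by-week interaction as a second continuous covariate in the primary model and in the 12-month UACR model. Do not replace the Visit 3 value with a plain average of the two visits.
3. Add a rule for a missing Visit 2 value, so that no patient drops out of the model for lack of a covariate. For example, fill it from the patient's Visit 3 value, blind to treatment.
4. Add a rule for which set counts after a repeat or re-screening, for example the last set before Visit 3.
5. Fix these choices before anyone on the analysis team sees unblinded Week 34 data.

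No extra sampling or patients are needed. If all five on-treatment visits up to Week 34 (Weeks 4, 8, 12, 20 and 34) enter the model, the second covariate adds five fixed-effect parameters. If that model does not converge, the natural first back-up is to drop the Visit 2 terms and return to the model now planned.
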